Descriptive analyses will be conducted to characterize high risk PCa census tracts compared to lower risk census tracts. Mapping the high risk census tracts will help us to determine how they are distributed within and around pre-defined Philadelphia neighborhoods (commonly used community names for each section of the city, Figure 2.) Those Philadelphia neighborhoods will become the target

neighborhoods for aims 2 and 3. Continuous variables will be analyzed with t-tests (or nonparametric alternative tests for variables without normal distributions) and categorical variables will be analyzed with frequency tables and chi square tests or Fisher's exact tests if any expected cell frequencies are small. Patient-level and neighborhood variables will be summarized for comparisons between high risk and lower risk neighborhoods to highlight factors that may be central topics of focus groups and intervention development. Correlations will be computed to examine the relationship between percent of cases with advanced disease and prostate-specific mortality rates. Regression modeling will allow us to determine significant trends in PCa incidence and mortality over time with and without adjustment for covariates such as the prevalence of risk factors including older age at diagnosis, African American residents and low neighborhood SES. We will also use the EpiQMS tool provided on the PA Department of Health website to determine age-specific incidence and mortality rates for Philadelphia. Generating maps of these data along with maps showing highest prevalence of PCa screening (CHDB data) will indicate where should target our focus groups and interventions for aims 2 and 3.

B2.f. Designation of Neighborhoods for Study Condition

Based on the GIS mapping results, the four neighborhoods in Philadelphia with the highest rates of late-stage PCa will be chosen to serve as study sites. Study condition (intervention or control) will be designated at the neighborhood level. Therefore, two of the sites will be designated as intervention neighborhoods and two will be designated as control neighborhoods. All men who live in the same neighborhood will receive the same intervention. All efforts will be made to ensure that the designations are done in a way that Intervention and Control neighborhoods are not geographically adjacent to each other, to avoid contamination of study messages among participants.

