Informed Consent and Baseline Survey: The health educator will obtain informed consent from each participant by reviewing the consent document and answering any questions about the study. After signing the consent document, participants will complete a brief pencil-and-paper baseline questionnaire. Items to be assessed at baseline include knowledge about prostate cancer and screening, attitudes towards screening, subjective norms about screening, decisional conflict about screening, and intentions to screen. Knowledge about prostate cancer and screening will be measured with a 17-item scale, recently validated with a sample of African American males. [18] The measure for decisional conflict will be constructed from O'Connor's Decisional Conflict Scale, a frequently used assessment for anxiety about decision making.[19] This scale includes a self-efficacy subscale that pertains to whether the participant feels 'a lot confident', 'a little confident', or 'not at all confident' about making an informed health decision. Demographic data related to age, race/ethnicity, family history of prostate or other cancer, and other pertinent health information will be collected. Additionally, contact information (telephone number(s), email address, and mailing address) for each participant will be collected to aid in maintaining communication with enrolled participants for post-survey completion.

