The target sample size is $n=200$ men. Since we anticipate 20% attrition, we will recruit and consent 240 evenly distributed across each of the 4 neighborhoods. In a local population similar to our target population, a previous prostate cancer screening decision making study [21] found that, compared to standard intervention controls, their decision support enhanced intervention lead to a 0.8 point increase ($SD = 1.5$) in knowledge on a 10-point scale. Assuming this in our target population, a type I error rate of 0.05, an intra-neighborhood correlation of 0.005 to 0.01, and that 4 to 10 neighborhoods will be sampled per group, the planned study should have approximately 80% to 94% power to detect this difference. In a similar prostate cancer screening shared decision making article [22], investigators found that their intervention lead to a 22% reduction ($SD = 0.15$) in prostate screening. Making similar assumptions as for the knowledge endpoint, we may be somewhat underpowered for detecting this difference in screening rates as the expected power would be approximately 50% to 67%. However, the primary goal is to increase knowledge about screening so that each man will make an informed decision taking into account his risk factors and personal preferences.

B.4.f. Results Dissemination

The study results will be disseminated to the neighborhood at the end of the project by multiple methods. Town hall meetings will be held in the targeted neighborhoods to explain the goals of the study and to provide a summary of results and additional PCa education to the community at-large. Next steps will be discussed, as well as ways to improve, sustain and expand targeted educational interventions around the Philadelphia region. Project newsletters and brochures will be made available to be shared with family and community members. The video developed during aim 2 for educational purposes will be shared at the town halls and will be made available on the internet for public education.

C. Potential Problems and Alternative Approaches

C.1. Geocoding

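### The stated 80% to 94% power for knowledge assumes 4 to 10 neighborhoods per group; the design has two per group, where the calculation that reproduces those figures gives about 40% to 46%

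*Combined protocol and SAP*

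**What the plan says.** Section B2.f assigns study condition by neighborhood: "two of the sites will be designated as intervention neighborhoods and two will be designated as control neighborhoods". Section B.4.b limits eligibility to residents of the four selected neighborhoods, and B.4.c repeats that all men in a neighborhood share one condition.

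Section B.4.e opens in agreement with this. It says "The target sample size is $n=200$ men" and, allowing for 20% attrition, "we will recruit and consent 240 evenly distributed across each of the 4 neighborhoods". It takes its planning effect from an earlier decision-support study, whose "intervention lead to a 0.8 point increase ($SD = 1.5$) in knowledge on a 10-point scale". It then adds "a type I error rate of 0.05" and an ICC of 0.005 to 0.01, and concludes on the basis that "4 to 10 neighborhoods will be sampled per group, the planned study should have approximately 80% to 94% power to detect this difference".

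For screening, the same paragraph makes similar assumptions, gives 50% to 67% power, concedes that this may be too low, and falls back on knowledge as the primary goal.

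Section B.4.d tests the hypotheses with mixed models that have a random intercept for neighborhood. Section B.4.c describes the instrument: "Knowledge about prostate cancer and screening will be measured with a 17-item scale".

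**The concern.** Four to ten neighborhoods per group means 8 to 20 in total. The trial will have four. Even the least favorable case in the power paragraph has twice as many clusters as the design, and no section provides for more.

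The number of clusters matters here because condition is assigned by neighborhood. With the total sample held at 200, fewer neighborhoods means more men in each, which raises the design effect. It also means fewer independent units from which to estimate between-neighborhood variation, which cuts the degrees of freedom.

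Knowledge is the only endpoint that the plan presents as adequately powered, and the plan leans on it after conceding that screening is not. If the figure belongs to a different design, the stated justification for the sample size does not apply to this trial.

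**Working it through.** **Inputs**

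- Analysed sample: 200 men, 100 per group (B.4.e).
- Effect: 0.8 points with SD 1.5, so d = 0.8/1.5 = 0.533 SD (B.4.e).
- Type I error 0.05 (B.4.e). Two-sided is assumed, as the plan does not say.
- ICC 0.005 to 0.01 (B.4.e).
- Neighborhoods per group, k: 4 to 10 in the power statement (B.4.e), 2 in the design (B2.f).

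**Formulas**

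- Men per neighborhood: m = 100/k.
- Design effect: DE = 1 + (m − 1) × ICC.
- Noncentrality: ncp = d / √(2 × DE / 100).
- Power: noncentral t with df = 2(k − 1), two-sided 0.05.

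**Step 1. Reproduce the plan's range**

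| k per group | ICC | m | DE | ncp | df | Power |
|---|---|---|---|---|---|---|
| 4 | 0.01 | 25 | 1.240 | 3.387 | 6 | 80.4% |
| 4 | 0.005 | 25 | 1.120 | 3.563 | 6 | 84.2% |
| 10 | 0.01 | 10 | 1.090 | 3.612 | 18 | 92.7% |
| 10 | 0.005 | 10 | 1.045 | 3.689 | 18 | 93.7% |

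The extremes, 80.4% and 93.7%, match the stated 80% and 94%. Other methods over the same k and ICC ranges do not:

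- normal approximation with the design effect: 92.3% to 95.8%
- individual-level df of 198: 92.1% to 95.7%
- one-sided t test: 90.8% to 97.1%
- 240 men analysed: 85.5% to 96.7%
- no clustering: 96.5%

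**Step 2. Change only k, to the design's value**

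| k per group | ICC | m | DE | ncp | df | Power |
|---|---|---|---|---|---|---|
| 2 | 0.01 | 50 | 1.490 | 3.090 | 2 | 40% |
| 2 | 0.005 | 50 | 1.245 | 3.380 | 2 | 46% |

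A simulation of cluster means (200,000 replicates per scenario) agreed to within 0.2 percentage points.

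**Step 3. Vary the number analysed (k = 2)**

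- 240 consented less 20% is 240 × 0.8 = 192 men, 48 per neighborhood: 39.6% to 44.6%.
- All 240 retained, 60 per neighborhood: 43.7% to 50.0%.

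**Step 4. Find the source of the loss**

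At ICC 0.01, going from k = 4 to k = 2 lowers ncp only from 3.387 to 3.090, while the critical t rises from 2.45 (6 df) to 4.30 (2 df). With ICC set to 0, so that there is no design-effect penalty, power on 2 df is still only 52.5%. The degrees of freedom do most of the damage.

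**Step 5. Detectable effect**

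Solving for 80% power at k = 2 with 200 men gives 0.89 SD (ICC 0.005) and 0.98 SD (ICC 0.01). On the source study's scale these are 0.89 × 1.5 = 1.3 and 0.98 × 1.5 = 1.5 points, against the 0.8 planned.

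**The case against.** **The method is inferred.** The plan gives no formula, sidedness or degrees of freedom, and B.4.d names no df method for the mixed model. This stands as a qualification. The match at both ends, and the failure of the alternatives, make the inference well supported. The conflict over the number of neighborhoods needs no formula at all.

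**Individual-level degrees of freedom would rescue the power.** With 198 df, power at k = 2 is 87% to 92%. But that method gives 92% at k = 4 and ICC 0.01, where the plan says 80%, so it is not the calculation behind the stated figure. It would also claim more precision than four clusters can supply.

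**The word might mean census tracts or sites.** The documents do not say so. Section B.2.b merges adjacent high-risk tracts within a neighborhood into one, and B.4.e itself counts four neighborhoods. Smaller units would not add assigned units either, because condition is set by neighborhood.

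**Covariate adjustment could add precision.** Baseline knowledge is collected, and adjustment for confounders is planned. This is fair, but the documents give no correlation from which to size it, and it adds no clusters. To reach 80% power for 0.8 points, the residual SD would have to fall from 1.5 to between 0.8/0.98 = 0.82 and 0.8/0.89 = 0.90, if the ICC stayed unchanged. That means covariates explaining roughly 64% to 70% of the variance.

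**Stronger readings that the documents do not support.** A reader might infer that the 17-item scale lowers power further, by keeping 0.8 raw points while stretching the SD to 1.5 × 1.7 = 2.55. That rescales one quantity and not the other. Rescaling both gives 1.36/2.55 = 0.53 SD, as before. What remains is only that the conversion is unstated. A reader might also quote lower power at ICCs above 0.01. Those values are not in the plan and would be a reviewer's sensitivity analysis.

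**Conclusion.** The power statement for knowledge is wrong as written. Its arithmetic is reproducible; the fault is an input that contradicts the design. For two neighborhoods per group and the plan's other inputs, power is about 40% to 46% with 200 men, or 40% to 45% with 192, in place of 80% to 94%. The detectable effect is about 0.9 to 1.0 SD in place of 0.53 SD.

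This rests on a two-sided test, cluster-level degrees of freedom and an unadjusted comparison at a single time point. The first two are inferred from the match to the plan's figures; the third is a simplification.

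A reader might go further and conclude that the knowledge comparison must be abandoned as a test, or that a null result would be taken as evidence against the intervention. The documents establish neither. They show that the stated power does not belong to this design.

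The screening figure of 50% to 67% rests on similar assumptions and is open to the same doubt. No corrected value is offered, because the plan gives no baseline screening rate.

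**What to change.** 1. Reconcile the number of neighborhoods in B.4.e with B2.f, B.4.b and B.4.c.
2. If the design stays at two neighborhoods per group, restate the knowledge power as about 40% to 46% for 0.53 SD, and give the detectable effect of about 0.9 to 1.0 SD.
3. State the formula, sidedness, degrees of freedom and analysed number. The plan gives 200 analysed, but 240 less 20% is 192.
4. Give the effect in SD units, since the source scale has 10 points and the trial's has 17 items, and state the equivalent on the trial's scale.
5. Recompute the screening power for two neighborhoods per group, showing the assumed baseline rate.
6. Label any ICC above 0.01 as an added sensitivity value.

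Correcting the text needs no new data; its cost is a less favorable power figure. Describing the knowledge comparison as preliminary is optional and would cost more than wording, since it touches Hypothesis 3a and the stated primary goal. Adding neighborhoods is the other route, and is a change of design.

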B.3. Aim 2: To develop a targeted PCa screening intervention for the high risk neighborhoods using a mixed-methods approach.

The study team will develop a behavioral intervention informed by neighborhood-level data and the health experiences of men living in the pre-selected neighborhoods. The intervention will be developed to be culturally sensitive to the context of high risk urban populations using data from previous research, local context, and pilot testing to refine intervention components. [9]

B.3.a.Theoretical Framework

The Theory of Planned Behavior (TPB) posits that an individual's intention to perform a given behavior, in this case one's intention to be screened for prostate cancer, is based on one's attitudes toward the behavior (positive or negative evaluation of performing the behavior), subjective norms (perception of the social pressures to perform or not perform the behavior), and one's perceived behavioral control (perception of the ability to perform the behavior. [10] Behavioral beliefs produce a favorable or unfavorable attitude toward the behavior; normative beliefs result in perceived social pressure or subjective norm; and control beliefs give rise to perceived behavioral control. The TPB is a useful model for predicting a wide range of behaviors and behavioral intentions [11] and has been used in the context of prostate cancer education in the past. [12-14] Therefore, the messages in the health education curriculum will aim to increase positive attitudes towards prostate cancer screening, create favorable subjective norms related to screening, and improve perceptions of behavioral control over the screening decision.

B.3.b. Development of Study Materials

MEE's Creative Team will develop a series of educational materials for use during participant recruitment and the health education sessions. These materials may include: a summary presentation to outline the project and its incentives to participants; a one-page, formal Partnership Agreement signed by each participating study site; posters and "Ask Me About Prostate Health" buttons that can be prominently displayed and worn by members of partner sites, helping to publicize the project; a customized, user-friendly curriculum booklet for the small group education sessions; and a project Facebook page and Website.

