Inclusion Criteria: Men ages 40-69 who currently reside in one of the four selected high risk neighborhoods will be eligible to participate in the study. This age range was selected based upon current screening recommendations for high-risk men. Additionally, the literature suggests that, when asked what age group might be most in need of prostate health information, men in this age group were frequently identified because they may not understand that they are susceptible to prostate cancer. [16, 17]

Exclusion Criteria: Men who do not reside in one of the four neighborhoods, who self-report that they have previously been diagnosed with prostate cancer, or who have had prostate cancer screening (PSA or DRE) within the past 12 months will be excluded from participating in the study.

B.4.c. Study Intervention

Because the level of designation for study condition will be at the neighborhood level, all men who reside in the same neighborhood will be in the same condition (intervention or control). Community health educators will go to participating study sites within the selected neighborhoods in pairs and will complete the following steps:

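### The 50% to 67% power for screening cannot be reproduced from the stated 22% reduction with SD 0.15, and it assumes 4 to 10 neighborhoods per group where the design has 2

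*Combined protocol and SAP*

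**What the plan says.** Section B.4.e (Power Analysis) sets the size of the study: "The target sample size is $n=200$ men", and "Since we anticipate 20% attrition, we will recruit and consent 240 evenly distributed across each of the 4 neighborhoods". For knowledge it assumes a 0.8-point gain with SD 1.5, "a type I error rate of 0.05, an intra-neighborhood correlation of 0.005 to 0.01", and that "4 to 10 neighborhoods will be sampled per group", and reports 80% to 94% power.

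For screening it takes from a cited shared decision-making article an intervention that "lead to a 22% reduction ($SD = 0.15$) in prostate screening", carries over similar assumptions, and concludes that "we may be somewhat underpowered for detecting this difference in screening rates as the expected power would be approximately 50% to 67" percent. It gives no control screening rate. It does not say whether 22% is absolute or relative, or what the SD of 0.15 describes. It then ranks knowledge first.

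Elsewhere:

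- Section B2.f assigns two neighborhoods to intervention and two to control.
- Table 2 (section B.1) lists PSA screening among the primary outcomes of Aim 3, while Aim 4 (section A.1) only observes screening rates.
- Section B.3.a says the messages aim to "increase positive attitudes towards prostate cancer screening, create favorable subjective norms related to screening".
- Section B.4.b says that men "who have had prostate cancer screening (PSA or DRE) within the past 12 months will be excluded".

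**The concern.** The contradiction shows before any software is run. The knowledge effect is 0.8/1.5 = 0.53 SD and is given 80% to 94% power. The screening effect, read as written, is 0.22/0.15 = 1.47 SD, which is 2.75 times as large. With the same number of men, clusters and ICC, a larger standardized effect must have more power, yet the plan reports less.

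An SD of 0.15 is also odd for a yes/no outcome. It requires p(1-p) = 0.0225, a rate near 2.3% or 97.7%.

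At stake is whether a reader can rely on the stated power for an outcome that Table 2 calls primary, and whether the admitted shortfall in power is as mild as the plan suggests.

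**Working it through.** **Inputs.** From section B.4.e: 200 men (taken as 100 per group, given the even split), alpha 0.05, ICC 0.005 to 0.01, k = 4 to 10 neighborhoods per group. From section B2.f: k = 2. The plan names neither the power method nor the sidedness. I assume a two-sided cluster-level t-test and check it against the knowledge figure.

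**Formula.** With m = 100/k men per neighborhood and standardized effect d:

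- standard error of d: sqrt(2 × (1 + (m − 1) × ICC) / (k × m))
- power from the noncentral t with 2(k − 1) df and noncentrality d / standard error

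**Step 1: reproduce the knowledge power.** d = 0.8/1.5 = 0.533.

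- k = 4, m = 25, ICC 0.01: design effect 1.24, standard error 0.1575, noncentrality 3.39, 6 df, power 80.4%.
- k = 10, m = 10, ICC 0.005: design effect 1.045, standard error 0.1446, noncentrality 3.69, 18 df, power 93.7%.

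These match the stated 80% and 94%, so the method is a fair reading of what was done.

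**Step 2: apply it to screening.** For the binomial rows, SD = sqrt((p1(1 − p1) + p2(1 − p2))/2). All control rates are my assumptions.

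| Reading | d | k = 4, ICC 0.01 | k = 10, ICC 0.005 |
|---|---|---|---|
| Stated in the plan | not given | 50% | 67% |
| 0.22 with SD 0.15 | 1.467 | >99.9% | >99.9% |
| 22 points, 30% to 8% | 0.584 | 87% | 97% |
| 22 points, 61% to 39% (lowest power) | 0.451 | 67% | 84% |
| 22 points, 90% to 68% | 0.561 | 84% | 96% |
| 22% relative, 25% to 19.5%, binomial SD 0.415 | 0.133 | 11% | 14% |
| 22% relative, 76.5% to 59.7%, binomial SD 0.458 | 0.367 | 50% | 67% |
| 22% relative of 25%, SD 0.15 (0.055/0.15) | 0.367 | 50% | 67% |

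The stated range corresponds to d of about 0.367, one quarter of 1.467. An absolute 22-point drop never reaches 50%; its lowest values are 67% and 84%. Its within-group SD is at least 0.29 (22% to 0%), so 0.15 cannot be the individual SD on that reading. Treating 0.15 as the SD of neighborhood rates gives 41% (k = 4) to 87% (k = 10), which does not match either. Only the last two rows match, and both need a control rate that the documents do not give.

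**Step 3: use the design's 2 neighborhoods per group.** k = 2, m = 50, 2 df; standard error 0.1726 (ICC 0.01) or 0.1578 (ICC 0.005).

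| Reading | ICC 0.01 | ICC 0.005 |
|---|---|---|
| 22 points, 30% to 8% | 46% | 51% |
| 22 points, 61% to 39% | 32% | 36% |
| 22 points, 90% to 68% | 43% | 49% |
| 22% relative, 20% to 15.6% | 7% | 7% |
| 22% relative, 60% to 46.8% | 15% | 17% |
| 22% relative, 76.5% to 59.7% | 24% | 27% |

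Even the reading that matches the plan's range at 4 to 10 per group falls to 24% to 27% at 2 per group. Taking 0.22/0.15 literally would still give 97.2% to 98.6%, so the low figures depend on replacing the SD of 0.15 by a binomial one.

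**The case against.** The best defense is that the plan never says the 22% is absolute. As a relative reduction with binomial variance, a control rate near 76.5% yields the stated range. This stands, and it rules out a stronger reading that a reader might infer: that 50% to 67% is impossible because a 0.22 difference would need an SD of 0.60, above the 0.5 maximum for a yes/no outcome. That holds only for an absolute difference. The defense does not rescue the text as written, because the match needs an unstated control rate and ignores the SD of 0.15. The other match keeps 0.15 but needs an unstated rate near 25%, where the binomial SD is 0.415.

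A reader might also infer that borrowing a reduction, when the messages favor screening, is an arithmetic error. It is not. A two-sided test has the same power for a rise or a fall between the same two rates, Aim 4 has no directional hypothesis, and the stated goal is an informed choice. It is a gap in the rationale only. Likewise, the remark that recently unscreened men would need control uptake of at least 22% applies only to an absolute fall.

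Finally, the mismatch between 2 and 4 to 10 neighborhoods is a separate defect that also affects knowledge, and the plan already admits limited power for screening. Both are true. For that reason Step 2 keeps the plan's own 4 to 10, and the failure to reproduce does not depend on Step 3.

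**Conclusion.** The stated screening power cannot be reproduced from the inputs given beside it. Literally read they give above 99.9%; an absolute 22-point drop with binomial variance gives at least 67% to 84%; and the stated 50% to 67% requires a relative scale plus a control rate found nowhere in the documents.

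At the design's 2 neighborhoods per group, power is about 32% to 51% (22 points absolute, control 30% to 90%) or 7% to 17% (22% relative, control 20% to 60%), so the plan's mild wording may understate the shortfall. These figures rest on assumed control rates, 100 analyzed men per group, the plan's ICC range and a test on 2 df. A large-sample test that ignored the small number of neighborhoods would show higher nominal power.

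Severity is moderate. The sample size rests on knowledge, whose power does reproduce under the plan's stated 4 to 10 neighborhoods, and no hypothesis on screening uptake depends on this figure. The documents do not support the inference that the sample size fails because of it.

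**What to change.** In section B.4.e, delete the 50% to 67% figure and the SD of 0.15. Then choose one of two routes:

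1. Restate the power. Give an assumed control uptake at 4 months, the intervention uptake, whether the difference is absolute or relative, and the expected direction. Use binomial variance and 2 neighborhoods per group, and show a range of control rates.
2. Declare Aim 4 descriptive, reporting screening rates by group with confidence intervals and no powered test. This fits the aim's own wording. Table 2 must then be reconciled, since it lists PSA screening as a primary outcome.

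On either route, add a sentence explaining why a reduction was taken as the planning effect when sections B.3.a and B.4.c describe messages favorable to screening. The cost is protocol wording and, for the first route, a short recalculation; no change to recruitment or data collection is needed.
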